APPENDIX M. PHASE II QUESTIONNAIRE: ASSESSING PAPR FLOW RATE EFFECT	
APPENDIX N. PHASE III QUESTIONNAIRE: ASSESSING USER WORK RATE EFFECT	74
APPENDIX O. NPPTL DAILY POST-TEST EVALUATION	75
APPENDIX P. EMERGENCY DECISION MAKING PROTOCOL	77
APPENDIX Q. STUDY INVESTIGATORS	78
APPENDIX R. DELEGATION OF AUTHORITY LOG	811
APPENDIX S. IRS FORM W-9	83
APPENDIX T. TEST SUBJECT PAYMENT FORM	889
APPENDIX U. NPPTL GENERAL PHOTO RELEASE	900

PROTOCOL SUMMARY

This is a controlled study to examine methods for quantifying powered air-purifying respirator (PAPR) performance, usability, and flow rates, as well as to improve effectiveness in healthcare while maintaining device safety and efficacy. Tests will be conducted at the Centers for Disease Control and Prevention (CDC) campuses in Pittsburgh, PA with a sample size of 25 evaluable subjects, and up to 75 subjects enrolled. Subjects will be considered evaluable if they meet screening requirements and fall within an available NIOSH/NPPTL Bivariate Panel cell category to provide representation of facial sizing for the U.S. workforce (Zhuang et al., 2007), and complete all study interventions within at least one of three phases. **Phase I** of this study will collect baseline physiological data to determine typical work rates for ten exercises identified in healthcare, without wearing a PAPR. Subjects will complete **Phase II**, replicating the ten activities from Phase I, while trialing eight models of PAPRs at two flow rates (NIOSH minimum and a reduced rate below NIOSH minimum flow rate), to determine simulated workplace protection factor (SWPF) values. Phase III will include two exercise regimens comprised of three exercises each, and subjects will trial eight models of PAPRs with the flow rate held constant at NIOSH approved minimum standard rate, to determine work rate effect on SWPF values when exercise regimen is modified by task order, work rate, and time.

The goal of this project is to aid development of a) improved test methods for quantifying PAPR performance and usability, and b) gain better understanding of the relationships between flow rate, work rate, respiratory inlet covering (RIC) design and performance. The SWPF test methods may be used in the future to assess next generation PAPR prototypes. Specific aims include: 1) to determine the effect of PAPR airflow rates on SWPFs; 2) to evaluate the effect of work rates on SWPF; and 3) to evaluate the effect of PAPR RIC design on SWPF. These three variables will also be assessed in terms of comfort and usability.

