4.1 Inclusion Criteria

- Ability to understand, the willingness to participate, and the completion of a written informed consent document
- Understands spoken and written English language as required for consent and instruction
- Age > 18 years old and < 55 years old
- OSHA/NPPTL Medical Evaluation Form completed by the participant and reviewed/signed by a U.S. licensed health professional such as a registered nurse or certified registered nurse practitioner (Appendix D.)
- If a subject reports "yes" to any medical condition listed on the OSHA/NPPTL Medical Evaluation Form (Appendix D.) in Part B for Questions 2, or 10 to 15, a Certified Registered Nurse Practitioner/Registered Nurse must review the subject's current and past medical history and provide written documented clearance for the subject to participate.

- NPPTL Screening Medical Review completed by participant and U.S. licensed health professional (Appendix E.)
 - Two head and face measurements using a tape measure and calipers, values recorded on the anthropometric data form (Appendix J)
 - NIOSH/NPPTL Bivariate Panel (Fig. 2 and Table 2) facial measurements and cell category availability based on their allocation to provide representation of the US workforce (if a cell category is full the subject will be considered a screen fail, however can rescreen at a later date if a subject in their cell category is not considered evaluable).
 - Subject will pass fit testing for three models of tight fitting PAPRs, with sizes provided by the NIOSH/NPPTL Bivariate Panel
 - Subject completion of the Subject Data Form (Appendix F), including agreement to refrain from caffeine consumption 12 hours prior to and during testing and smoking 1 hour prior to and during testing
 - Complete maximal graded exercise testing with treadmill protocol (Appendix K) and achieve a maximal oxygen consumption **above** "Poor" category (e.g. Fair to Excellent categories required for inclusion) based on American College of Sports Medicine Fitness Categories for Maximal Aerobic Power (treadmill test)
 - Review of the NPPTL General Photo Release Form (Appendix U).

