6.0 SUBJECT DISCONTINUATION

Subjects may be removed from the study for the following reasons:

- Do not meet screening safety and/or inclusion eligibility. Note that for subjects whom complete facial measurements allocating them to a cell category that is full, they can be recontacted and re-screened in the event a registered subject in their cell category becomes unevaluable.
- New conditions that prevent the subject from wearing a PAPR or completing the study exercises
- New conditions that prevent the subject from completion of the study interventions and/or evaluations
- Adverse events experienced by the subject
- Subject decides to withdraw from the study
- Subject non-compliance with study requirements, confirmed by the site PI
- For any reason the PI deems is necessary to protect the safety, data integrity, and/or confidentiality of the subject

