The rationale for the inclusion of the supplement use question is to identify any additional risk factors such as pulmonary or cardiovascular problems (both exclusion criteria) that someone treats with supplements. It is also intended to identify supplements that a subject may be taking which could affect their heart and/or respiration rate or breathing patterns (e.g. caffeine). Today's market has so many supplements that claim to treat many different ailments or increase exercise performance. It is possible that participants who regularly exercise may take some supplement to enhance their workout. We are trying to identify anything a participant uses that could affect the study or increase their risk.

A supplement is any dietary treatment that is used to enhance one's health or performance. Ingredients of concern, but are not limited to, include caffeine, energy drinks, nicotine, Ma huang, Yohimbine, Ginseng, Ephedra, Khat, Licorice root, Bitter orange, Goldenseal, or any other supplement that could affect the subject's heart rate or blood pressure. Supplements not listed will be evaluated at the discretion of the U.S. licensed health professional.

As a part of the Subject Data form (Appendix F), completion of which is a required inclusion criterion, subjects will be asked if they are willing to refrain from caffeine consumption for 12 hours prior to and during testing and smoking 1 hour prior to and during testing. The rationale for asking participants to refrain from smoking for 1 hour prior to and during testing is based on the recommendation from TSI, Inc., the manufacturer of the PortaCount for fit tests. Failure to refrain from smoking could lead to false particle counts in the respirator due to residual smoke particles being exhaled by the wearer. Specific tobacco products participants must refrain from using are cigarettes, cigars, and electronic cigarettes. Participants are asked to refrain from caffeine consumption because it is a stimulant, therefore increasing the participant's heart rate and increases the risk of an adverse event. It could raise a participant's heart rate beyond the limitations for the study, causing test termination and the exclusion of the subject for that day.

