$HR \geqslant 90\%$ of measured HR_{max} for a period of at least one minute	X	X	X	X	X	
At the discretion of the investigator/ U.S. licensed health professional	X	X	X	X	X	
[CO ₂] in the PAPR \geq 6% of atmospheric by volume for a period greater than one minute			X	X		

Maximal aerobic capacity (VO_{2max}) of subjects is monitored as part of the screening process and to provide safety during study interventions. The screening maximal graded exercise test includes the determination of underlying cardiopulmonary issues that may exclude the subject for safety purposes. Additionally the Maximal Graded Exercise test will allow the study team to determine the level of exercise at which the subject reaches their maximal oxygen uptake (VO_{2max}). If VO_{2max} has been reached, as determined during screening, the study team will terminate the exercise and remove subject from study to promote safety. The maximal heart rate achieved at VO_{2max} is also measured during the maximal graded exercise screening test. If the subject reaches $\geq 90\%$ of their maximal heart rate (HR_{max}) over the course of one minute, the study test will be terminated and the subject removed from study for safety. For example, if the subjects HR_{max} is $190 \text{ b} \cdot \text{min}^{-1}$, the test would be terminated when the subjects HR reaches $171 \text{ b} \cdot \text{min}^{-1}$ over the course of one minute during testing. The procedure for the Maximal Graded Exercise Test, as well as monitoring from the metabolic cart, is described in Appendix K.

During Phases II and III, subjects will be breathing in a confined space with an expected increase in atmospheric CO₂, leading to a potential for CO₂ rebreathing. For this reason, a test termination criterion has been established as a function of in-mask change in CO₂ concentration from atmospheric levels. If the in-mask CO₂ concentration is greater than 6% of the atmospheric levels, for a period greater than one minute, the test will be terminated.

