8.0 STATISTICAL METHODS

8.1 Phase I Statistical Methods

For Phase I, mean VO₂ and HR values with 95% confidence interval will be calculated for each exercise. In this study phase, the data will be analyzed after all 25 subjects complete the first of three replicates so that each exercise will have 25 values calculated. If, after the first 25 subjects, the lower and upper bounds of the 95% confidence interval for the estimated population parameters are within the theoretically categorized work rates, then second and third replicates will not be needed.

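### In Phase I, a heart-rate stop removes a subject who can then be replaced, so hard-exercise means can be cut off at 90% of maximal heart rate, inside the band they are meant to identify

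*Protocol*

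**What the plan says.** **Evaluability.** The Protocol Summary requires subjects to pass screening, fit an open face-size cell "and complete all study interventions within at least one of three phases".

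**Consequence of a stop.** Section 7.4 says that when a subject reaches 90% of HRmax over one minute, "the study test will be terminated and the subject removed from study for safety". For VO2max it says "the study team will terminate the exercise and remove subject from study to promote safety". Table 7 applies the heart-rate criterion in screening and all three phases. It applies the VO2max criterion in screening and Phase I only. Section 7.3, explaining the caffeine restriction, gives a different result of exceeding the heart-rate limit: "causing test termination and the exclusion of the subject for that day".

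**Replacement.** Section 4.1 says a person turned away from a full cell "can rescreen at a later date if a subject in their cell category is not considered evaluable". Section 6.0 says such people can be "re-screened in the event a registered subject in their cell category becomes unevaluable", and Section 5.1 repeats this. Sections 3.3 and 3.4 let new subjects enter Phases II and III when earlier ones decline or lose eligibility.

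**Phase I analysis.** Section 8.1 analyses the data "after all 25 subjects complete the first of three replicates so that each exercise will have 25 values calculated". Section 3.2 averages each exercise over all 25 subjects and classifies it by Table 4, where Hard is 77-93% of maximal heart rate. Table 3 expects exercises 8, 9 and 10 to be Hard.

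**The concern.** Phase I exists to place each exercise in a work-rate category, using heart rate and oxygen uptake relative to each subject's maximum. The removal limit of 90% lies inside the Hard band, so a subject who performs a hard exercise correctly can be removed for showing the response the exercise was chosen to produce. If someone else then fills that cell and the mean is taken over 25 completers, the highest heart rates are missing from the mean by rule rather than by chance. The mean is truncated on the quantity being classified, and truncation from above can only lower it.

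At stake are the category given to a hard exercise near the 77% edge and the Section 8.1 decision on replicates 2 and 3. In Phases II and III, removal and replacement can leave a sample that tolerates hard work better than the intended one. The two accounts of what a heart-rate stop leads to also leave staff without a single rule.

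**Working it through.** **The plan's own figures.** Section 7.4's example reproduces: 0.90 × 190 = 171 b/min. So does the Phase II count: 25 × 8 × 2 × 2 = 800.

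**Inputs from the protocol.** Stop at 90% of HRmax; Hard band 77-93%; n = 25; a 95% interval using 1.96 that must lie inside the band (Sections 3.2 and 8.1).

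**Assumptions.** The protocol gives no spread of heart rate and no stop rate. I take %HRmax in a hard exercise as Normal with mean m and SD s, and treat the one-minute rule as a single cut at 90. That is a simplification, because classification uses a subject's average work rate.

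**Phase I formulas.** Let a = (90 − m)/s and L = φ(a)/Φ(a).
- Share stopped: 1 − Φ(a).
- Stopped subjects replaced: mean = m − sL, SD = s√(1 − aL − L²).
- Stopped subjects kept at 90: mean = Φ(a)(m − sL) + (1 − Φ(a))·90.
- Interval: mean ± 1.96·SD/√25.

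**Example, m = 78, s = 8.** a = 1.5, L = 0.1295/0.9332 = 0.139, and 6.7% are stopped. The mean is 78 − 8 × 0.139 = 76.9 if they are replaced, below the Hard edge of 77. If they are kept at 90 it is 0.9332 × 76.89 + 0.0668 × 90 = 77.8. A censored-normal fit (1,500 simulated sets of 25) averages 78.0.

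**Range of the fall in the mean.**

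| True mean, SD | Stopped | Fall if replaced | Fall if kept at 90 |
|---|---|---|---|
| 77, 6 | 1.5% | 0.23 | 0.03 |
| 78, 8 | 6.7% | 1.1 | 0.2 |
| 81, 8 | 13.0% | 1.95 | 0.5 |
| 83, 10 | 24.2% | 4.1 | 1.4 |

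**Effect on the interval rule, m = 81, s = 8.** The full sample gives 77.9-84.1 and the kept sample 77.7-83.3, both inside Hard. The replaced sample gives 76.5-81.6, which is not. The decision changes only for true means of about 79.4-79.7 (SD 6), 80.2-81.7 (SD 8) or 81.0-84.6 (SD 10). When it changes, replicates 2 and 3 are run.

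**Phase II exposure.** A completer does 8 models × 2 flows × 2 replicates = 32 tests. Take one hard exercise over its 32 bouts, with subject mean u ~ N(m, sb) and within-subject SD sw. The chance of completing is E[Φ((90 − u)/sw)^32]. For sb 6-8 and sw 2-4:
- m = 77: 7-28% removed; completers' mean %HRmax lower by 0.9-3.7 points.
- m = 73: 2-15% and 0.3-2.1 points.
- m = 69: 0.3-6% and 0.1-1.0 points.

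The last two means lie in Table 4's Moderate band (64-76), so they describe exercises milder than the plan expects. Nothing in the protocol links these shifts to SWPF.

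**The two accounts of a stop.** Section 7.4 removes the subject from the study, whereas Section 7.3 excludes the subject for one day. Under 7.3 the subject could return and none of the removal above would follow.

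**The case against.** The strongest reply is that bias requires the stopped subject's data to be left out, and the protocol nowhere says they will be. Evaluable status serves to fill a 25-person face-size panel, Section 5.1 even keeps screen failures' data, and analysis sets normally belong in an analysis plan. This stands in part: a reader might infer that partial data are deleted, and no text says so. But the protocol itself fixes completion, removal and replacement, and states Phase I as 25 values per exercise from subjects who complete the replicate. That leaves a replaced subject no stated place in the mean.

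Several stronger readings do not hold:
- **That a stop in Phase II or III reopens the cell.** A Phase I completer has already met the evaluable definition. Replacement then runs through the lost-eligibility wording of Sections 3.3 and 3.4.
- **That VO2max stops also select in Phases II and III.** Table 7 limits that criterion to screening and Phase I.
- **That the flow or work-rate comparison is biased.** Both are within subject. They would be affected only if stops depended on flow or model, or if tolerant subjects responded differently.
- **That a stop cannot be tied to a condition because Appendix O asks once per visit.** Under Section 7.4 the stopped test is the subject's last, so its model and flow can be identified.

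It is also fair that the Phase I harm is limited. Failing the interval rule costs only more replicates, and it changes only over a narrow range of true means.

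**Conclusion.** The point holds as a minor one. In Phase I, the stated rules allow hard-exercise means to be truncated at 90% of HRmax and so biased downward. Under assumed means of 77-83 and SDs of 6-10 the fall is about 0.2 to 4 points of %HRmax. The true size is unknown, because it depends on a heart-rate spread the protocol does not give and on a simplified one-minute rule. Oxygen uptake was not modelled. The probable consequence is a borderline misclassification or replicates that were not needed.

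In Phases II and III, removal with replacement can narrow the tested population to people who tolerate hard work. That bears mainly on the geometric mean and 5th-percentile SWPF. A reader might infer a biased SWPF from this, but neither its size nor its direction can be derived from the protocol, and none is claimed.

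The conflict between Sections 7.3 and 7.4 needs no assumption and should be resolved in any case.

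**What to change.** Keep every safety stop and make these changes:

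1. State one consequence for a heart-rate stop during a study test, and align Section 7.3 with Section 7.4. Same-day exclusion can be confined to caffeine non-compliance.
2. Define each phase's analysis set as every subject who starts a test in that phase, with all data up to the stop. In Phase I, keep the interrupted exercise's heart rate and VO2, flagged as stopped at 90% of HRmax or more and treated as censored.
3. Let a replacement add to the stopped subject's data, not displace them.
4. Analyse per-exercise log SWPF with a model that accepts incomplete subjects, such as a mixed model.
5. Tabulate stops with their reason by exercise, model and flow rate.

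If removal remains the rule, later tests will still lack the stopped subjects, but their earlier data will count and the loss will be visible.

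The cost is wording changes, slightly unbalanced data and one extra table. No extra procedures are needed.

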1.0 BACKGROUND AND SIGNIFICANCE

A PAPR is a respirator that uses a battery-operated blower and a cartridge, canister and/or high efficiency particulate air (HEPA) filter(s), to provide the wearer with purified air through a RIC. A RIC can be categorized into tight-fitting facepiece (TFF), loose-fitting hood/helmet, or a loose-fitting facepiece (LFF). NIOSH certification PAPR test requirements and conditions were established in 1972 (42 CFR 84). However, over the years, workplace conditions have changed, the need for advanced protection has evolved, and improvements in technology necessitate the updating of PAPR test requirements. Research is needed to progress existing test methods and to develop new evaluations for PAPR performance (PAPR protection), comfort of wearing, and ease of communication. This study will provide important data for standards development organizations (SDOs), manufacturers, and NIOSH certification processes to accommodate future PAPR design and safety. Studies have shown that some users rate current PAPR design as too heavy and noisy, especially in healthcare settings (IOM, 2015). This study will provide data that may aid in the development of smaller lightweight devices with the same particulate protections as presently required, to improve workplace utility for today's diverse workforce.

1.1 Current Standards and Definitions

NIOSH Respiratory Protective Devices Final Rule 42 CFR Part 84

On June 8, 1995 NIOSH published 42 CFR Part 84 Final Rule on Respiratory Protective Devices, replacing NIOSHs original 1972 30 CFR Part 11 Rule. The requirements in 42 CFR

84 added new respiratory filter efficiency classification categories for non-powered air-purifying particulate respirators. In order to continue the approval of PAPRs to existing requirements, NIOSH established subpart KK in the new 42 CFR Part 84 rule 2. By maintaining 30 CFR 11 requirements, PAPRs would continue to be approved based on pre-1970s concepts and knowledge. PAPR blower motors must deliver a minimum flow rate of 170 liters/minute (Lpm) (for loose-fitting) or 115 Lpm (tight-fitting) to meet 42 CFR Part 84 requirements.

OSHA Assigned Protection Factors 29 CFR Parts 1910, 1915, 1926 71: 50121-50192

In a final rule on OSHA's Respiratory Protection standard (Federal Register 63, 1998), OSHA reserved the provisions incorporating Assigned Protection Factors (APFs) (See 63 FR 1152; 29 CFR 1910.134; 71 FR 50122, August 24, 2006.) which went into effect on November 22, 2006 (71 FR 50122). The APF for PAPRs depends on the type of respiratory inlet covering (RIC) and ranges from 25 (using a loose-fitting facepiece or loose-fitting hood) to 1,000 (for a tight-fitting full-facepiece, or for a loose-fitting hood which has been demonstrated by the manufacturer to have protection performance of $\geq 1,000$.

OSHA Respiratory Protection Medical Evaluation 29 CFR 1910.134

OSHA's revised Respiratory Protection Standard (29 CFR 1910.134 and 29 CFR 1926.103) went into effect April 8, 1998. The standard replaces those adopted by OSHA in 1971. The mandatory OSHA Respirator Medical Evaluation Questionnaire standard was updated in 2012. In this protocol, the Appendix D "OSHA/NPPTL Respirator Medical evaluation questionnaire" is used for the medical screening of test subjects based on this requirement.

Table 1. Protocol Definitions

TERM	DEFINITION / VALUES	
Assigned Protection Factor (APF)	The APF for PAPRs depends on the type of respiratory inlet covering (RIC). Values: 25 for loose-fitting facepieces or loose-fitting hoods 1,000 for tight-fitting full-facepiece (or for loose-fitting hood which has been demonstrated by the manufacturer to have protection performance of ≥ 1,000)	
Flow Rate In the United States, to meet 42 CFR Part 84 requirements, PAPR blowers must proc NIOSH approved minimum flow rate. Values: 170 liters/minute (Lpm) for loose-fit facepieces and 115 Lpm for tight-fitting facepieces		
Hood	A respiratory inlet covering that completely covers the head/neck and may cover portions of the shoulders and torso.	
Helmet	Differs from a hood only in that it provides a rigid head covering	
Loose-fitting facepiece (LFF)	A respiratory inlet covering that is designed to form a partial seal with the face. Value: loose-fitting inlet coverings are used on supplied air respirators (SAR) as well as PAPRs. In the U.S., the minimum airflow for LFFs is 170 L/min (CFR, 1995).	
Program Protection Factor (PPF)	An estimate of the respiratory protection provided to a worker in the context of a specific respirator program.	
Simulated Workplace Protection Factor (SWPF)	SWPF is deduced by measuring a test atmosphere concentration outside (Co) while also testing the inside (Ci) of a properly functioning respirator in a laboratory using test exercises designed to simulate work. Value: Calculated as 0 to continuous, and is expected to at minimum be equivalent to APF value designated for the device (at least 25 or 1000 for PAPRs)	

Workplace Protection Factor (WPF)	A measure of the protection provided in the workplace, under the conditions of that workplace, by a properly selected, fit tested and functioning respirator while it is correctly worn and used.
U.S. licensed health professional	An individual who is qualified by education, training, and licensure who performs a professional service within his/her scope of practice.

